12.3 Study duration

Recruitment of patients will continue until 100 patients are recruited and undergo TBM. The study duration will be extended as necessary until this target is met across all centres.

The study will remain open until the last patient to be recruited has completed their final 60 month follow-up. Thereafter, end of trial definition will be dependent on resolution of all data queries and completion of database entries in preparation for final statistical analysis and subsequent publication. Once these stages have been reached and the study paperwork is ready for archiving, a 'Declaration of End of Study Form' will be sent to RMH R&D and to the Research Ethics Committee (Health Research Authority) notifying them that the study is now concluded. A summary of the final research report will be provided to the Committee within 12 months of the conclusion of the study. This will report on whether the study achieved its objectives, summarise the main findings, and confirm arrangements for publication or dissemination of the research including any feedback to participants.

Summary of project timings (correct at time of drafting v2.2)

Date	Activity
Dec 2018	First draft of protocol
Jan 2019	Protocol submission to sponsor (CCR)
Feb 2019	CCR review
May 2019	Submission via IRAS
July 2019	REC/HRA approvals
Nov 2019	Opening of first sites
March 2020	COVID-19 disruption
October 2023	Completion of recruitment
October 2028	Completion of 60 month follow up for all patients

12.4 Analysis methods

Descriptive analysis only is anticipated. The rate of CH and SSS pick up will be reported in the overall specimens and separately in the sub-group of surgical methods with 95% confidence intervals. The pain scores and swallow recovery with MDADI scores will be reported using mean/median and standard deviation or range as appropriate at each time point of 0, 3 weeks, 6 weeks, 3 months, 6 months and 12 months, 24 months, 36 months, 48 months and 60 months. Similarly, score change between time points will be summarized in the same way. The primary and secondary analysis will be done when the complete sample size is recruited and last patient on the study completed all follow-ups.

Molecular data analysis

Detailed description of the molecular analysis methodology is beyond the scope of this protocol.

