Human papilloma virus (HPV) is thought to play a significant role in many of these cancers presenting as CUP.[6,7] Smaller or involved primary foci are known to be more common in HPV related cancers which may be contributing to the apparent incidence of these unknown primaries, or occultomas as they may also be called. A histological technique called step serial sectioning (SSS) allows examination of tissue specimens in greater detail than conventional histology. It has not previously been used to investigate the primary site in head and neck cancer but the oropharyngeal tissues that potentially harbour these small primaries make a sensible target to pioneer its usage. It is hypothesised that utilising SSS on tonsillectomy and TBM specimens may increase the identification rate of the primary site and may subsequently affect recommended management.

Currently, we do not understand why some cancers present with cervical metastases with no evident primary site. There has been an explosion in genomics research in many cancers, but this remains an understudied area in head and neck cancer. There are currently no treatments available to patients with head and neck cancer based on genomic insights. This study aims to begin to address the unmet need of patients who present with these poorly understood cancers and to provide a starting point for more detailed investigations into the relationships between cancer genomics and clinical outcomes.

6 Study aim and objectives

6.1 Aim:

To understand the current management of suspected HNSCCUP patients undergoing TBM in the UK, including adequacy of current histology, functional and oncological outcomes, and disease biology.

6.2 Primary objective:

- To establish if step serial sectioning (SSS), compared to conventional histology, improves identification of a primary site in TBM and tonsil specimens in suspected HNSCCUP.

6.3 Secondary objectives:

1. To compare the pick-up rate of primary cancers in TBM specimens between surgical methods (robotic vs laser vs endoscopic).
2. To prospectively evaluate swallowing function and pain scores after TBM.
3. To understand patient views and experiences of undergoing TBM for suspected HNSCCUP.
4. To report time-to-event data for local, regional and distant disease recurrence, and mortality.
5. To assess the molecular makeup of patients with suspected HNSCCUP undergoing TBM.

7 Study design and setting

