9.7 Handling of tissue specimens and histological processing

All tissue will undergo conventional histological processing at the local site and will be used to influence patient management by the local team according to local practices. The following tissues will then be requested to be sent by the local teams to RMH for further analysis:

- Oropharyngeal tissues from diagnostic surgeries attempting to identify the primary site (i.e., TBM specimens, and tonsils, if available)
- Cervical nodal specimens, from the diagnostic neck biopsies (fine needle aspiration cytology and/or core biopsies) and/or therapeutic neck surgeries, if available
- A buccal swab and/or blood sample (for germline DNA)

Where SSS is indicated (TBM and tonsil specimens, if available) the MOSES team will then send these tissues onto the RVI. Appropriate tissue handling practices will be observed. RMH uses FreezerPro Laboratory Management Software to facilitate handling and tracking of tissue specimens.

Anonymised histopathology reports will be requested from local centres. The macroscopic description will be used to orientate the submitted tissue blocks undergoing step serial sectioning.

Step serial sectioning

The paraffin blocks supplied from TBM and tonsil specimens will undergo step serial sectioning using the following method:

- Steps every 0.5mm with five serial 4 μ m sections taken.
- Each block will be processed in this way until the material is consumed.
- Slides will be stained with haematoxylin and eosin stain (H&E) and examined for signs of SCC.
- If an SCC is identified, then serial sections 2 and 4 will be submitted for HPV testing (p16 immunohistochemistry and high-risk HPV DNA in situ hybridisation).
- Serial sections 1 and 5 will be retained for repeat tests if required.
- The pathologist will compose a report and complete the relevant sections of the CRF.
- Unused material will be returned to the contributing centres if desired. Some material may be retained for further study, as detailed in the PIS and ICF.

Exploratory molecular analysis

Patients will be asked to provide buccal swabs and/or blood samples for germline DNA analysis. These samples may be provided at any time point following recruitment.

Packaging and sending

All MOSES blood and/or buccal swab samples should be collected, labelled, stored and shipped as detailed in the **MOSES Sample Collection Manual**.

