12.1 Sample size

No a prior sample size calculation was performed as initial funding limited recruitment to analysis of 60 specimens to undergo SSS. Meta-analysis shows a pickup rate of 58% for this cohort. We anticipate a potential increase pick up rate of around 10%.

- With 60 specimens, the 95% confidence interval boundaries around the pickup rate are +/- 12.6% for 58% and +/-11.4% for 68%.

In anticipation of further funding, our sample size is increased to 100 to give greater confidence in the effect size.

- With 100 specimens, the 95% confidence interval boundaries around the pickup rate are +/- 9.8% for 58% and +/-9.0% for 68%.

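### The primary objective is the gain of SSS over CH in the same specimens, but the plan gives no interval for that gain and no CH-by-SSS table

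*Protocol*

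**What the plan says.** Protocol Section 6.2 sets a comparative primary objective: "To establish if step serial sectioning (SSS), compared to conventional histology, improves identification of a primary site in TBM and tonsil specimens".

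Section 9.7 makes the comparison paired. First, "All tissue will undergo conventional histological processing at the local site"; then "The paraffin blocks supplied from TBM and tonsil specimens will undergo step serial sectioning". SSS is cut from the blocks that come back after CH, in this pattern: "Steps every 0.5mm with five serial" sections of 4 µm, until the block is used up.

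Section 12.4 describes the primary analysis: "Descriptive analysis only is anticipated. The rate of CH and SSS pick up will be reported in the overall specimens". It adds the same rates by surgical method, with 95% confidence intervals.

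Section 12.1 takes 58% as the existing pick-up rate and states "We anticipate a potential increase pick up rate of around 10" per cent. It explains the larger target: "our sample size is increased to 100 to give greater confidence in the effect size". The precision it then shows ("With 100 specimens, the 95% confidence interval boundaries around the pickup rate are") is ±9.8% at a rate of 58% and ±9.0% at a rate of 68%. Both figures concern a single rate.

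**The concern.** The objective is about a difference, and the plan attaches uncertainty only to its two components. A reader can subtract one rate from the other, but cannot derive the uncertainty of the difference, because that depends on how the two methods agree case by case.

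If every CH-positive case counted as found under SSS too, the two rates would be enough: all discordance would run one way, and both the paired interval and the SSS-only yield would follow. The Protocol does not state that rule, and its method does not guarantee it. SSS reads what is left of the block after CH and takes 20 µm (five 4 µm sections) at each 0.5 mm step, so a small focus seen on CH may not reappear.

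Two things are at stake. From the planned output the only available interval for the gain is the unpaired one, which is too wide over the range examined below and can hide a gain that the data support. And the case for 100 specimens rests on confidence in an effect size whose precision is never shown. Section 12.8 expects any increase in pick-up to influence adoption of SSS and to form the basis of a later trial. Both uses need the gain and its uncertainty.

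**Working it through.** **Inputs.** CH rate 58%, SSS rate 68%, hence a gain d = 0.10; n = 60 and n = 100 (all Section 12.1). Let b be the share of cases SSS-positive/CH-negative and c the share CH-positive/SSS-negative, so b = 0.10 + c. The Protocol does not give c; I assume 0 to 10%.

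**The plan's own figures.** The four half-widths in 12.1 match the upper arms of exact (Clopper-Pearson) intervals at whole counts:

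| Count | Upper arm (points) | Stated | Lower arm (points) |
|---|---|---|---|
| 35/60 | 12.60 | 12.6 | 13.45 |
| 41/60 | 11.41 | 11.4 | 13.29 |
| 58/100 | 9.80 | 9.8 | 10.29 |
| 68/100 | 8.98 | 9.0 | 10.08 |

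They are reproduced, and they describe single rates only. At n=100 the two exact intervals are 47.7–67.8% and 57.9–77.0%. They overlap widely, which says little about a paired gain.

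**Ignoring the pairing.** Half-width = 1.96·√(0.58·0.42/n + 0.68·0.32/n) = 1.96·√(0.4612/n).
- n=100: 13.3 points, interval −3.3 to 23.3.
- n=60: 17.2 points, interval −7.2 to 27.2.

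**Respecting the pairing (Wald).** Half-width = 1.96·√((b + c − d²)/n). With b = 0.10 + c and d² = 0.01 this is 1.96·√((0.09 + 2c)/n).

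| c | b | n=100: half-width, 95% CI | n=60: half-width, 95% CI |
|---|---|---|---|
| 0 | 10% | 5.9, 4.1 to 15.9 | 7.6, 2.4 to 17.6 |
| 2% | 12% | 7.1, 2.9 to 17.1 | 9.1, 0.9 to 19.1 |
| 5% | 15% | 8.5, 1.5 to 18.5 | 11.0, −1.0 to 21.0 |
| 10% | 20% | 10.6, −0.6 to 20.6 | 13.6, −3.6 to 23.6 |

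At n=100, Newcombe's paired limits agree with these to within 0.4 point.

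**When the lower limit reaches zero.** Set 0.09 + 2c = n·(0.10/1.96)².
- n=100: 0.09 + 2c = 0.2603, so c = 8.5%.
- n=60: 0.09 + 2c = 0.1562, so c = 3.3%.

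This is a concrete gain from moving from 60 to 100 specimens, and single-rate half-widths cannot show it.

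**When the unpaired interval is too wide.** It exceeds the paired one while 0.09 + 2c < 0.4612, that is, while c is below 18.6%. This covers the whole assumed range.

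**SSS-only yield among CH-negative cases.** At n=100 there are 100 − 58 = 42 CH-negative cases. The same pair of rates, 58% and 68%, fits all of these:

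| c | SSS-only cases | Yield | Exact 95% CI |
|---|---|---|---|
| 0 | 10/42 | 23.8% | 12.1–39.5% |
| 2% | 12/42 | 28.6% | 15.7–44.6% |
| 5% | 15/42 | 35.7% | 21.6–52.0% |
| 10% | 20/42 | 47.6% | 32.0–63.6% |

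The two marginal rates cannot tell these apart.

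**The case against.** **The SAP may cover this.** An interval method for matched proportions and a table layout are ordinary SAP content, and 12.4 excludes neither. That would settle the matter if the Protocol had deferred the primary analysis. Instead it states the output as two separate rates, and 12.1 supports the sample size with a precision statement that does not match the objective. Section 12.1 needs correcting whatever an SAP says.

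**The Protocol leans towards additive counting.** Section 12.5 speaks of cancers missed by CH, 12.8 of primaries found by SSS beyond CH, and the text just before Section 16 of new or additional carcinomas. No passage mentions a CH-only case. This makes a small c plausible, but it is not a counting rule, and 9.7 does not rule out CH-only cases.

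**The upper end of the range is stretched.** Blocks are stepped until consumed, and c = 10% would mean about 10 of 58 CH-positive cases (17%) negative on SSS. That is fair: 10% is an upper illustration. At n=100 the paired interval excludes zero at 0, 2 and 5%. This strengthens the case for reporting it, since the unpaired interval includes zero at the same rates.

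**The consequence is limited.** The study is descriptive, both results are on the CRF (Section 9.4), and the unpaired interval errs towards caution. All true, and the reason this is not graded higher. But a 2x2 table and an interval for a difference are descriptive too, and 12.4 already plans to summarise changes in pain and swallowing scores.

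**Conclusion.** The concern holds and should be fixed. The Protocol asks a paired, comparative question and plans two marginal rates. At its own 58%, 68% and n=100, the interval a reader could build is 10 ± 13.3 points, whereas the paired one is between ± 5.9 and ± 10.6. The SSS-only yield is left open between 23.8% and 47.6%.

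The paired figures rest on an assumed CH-only share of 0–10%, which the Protocol does not give, and on one CH and one SSS result per unit. If CH-positive cases are always counted as found, c is zero and the two rates suffice, but the Protocol would have to say so. No data are lost; what is missing is the reporting of the gain and the matching precision statement.

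**What to change.** **Section 12.4.**
- Report the CH-by-SSS 2x2 table.
- Report the paired difference (SSS minus CH) with a 95% confidence interval for matched proportions, for example Newcombe's.
- Report the SSS-only yield among CH-negative cases with an exact interval.
- State how a CH-positive/SSS-negative case is counted.
- Keep the two marginal rates. No hypothesis test is needed.

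**Section 12.1.** Restate precision for the paired difference over a declared discordance range. Using the figures above, 100 specimens would estimate a 10-point gain to within ± 5.9 to ± 10.6 points for a CH-only share of 0 to 10%.

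**Helpful alongside.** Name the unit of the table, since 12.1 and 12.4 count specimens and 12.3 counts patients. If the unit is the patient, list additional foci found by SSS separately, because Section 3 expects multi-focal primaries.

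**Cost.** Wording in two sections and one counting rule; no extra data, patients or procedures. The one drawback is that the restated precision depends on an assumed discordance range, which should be labelled as such.

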Objectives	
Primary:
 
 To establish if step serial sectioning (SSS), compared to conventional histology, improves identification of a primary site in TBM and tonsil specimens in suspected HNSCCUP. 
Secondary:
 
 To compare the pick-up rate of primary cancers in TBM specimens between surgical methods (robotic vs laser vs endoscopic). To prospectively evaluate swallowing function and pain scores after TBM. To understand patient views and experiences of undergoing TBM for suspected HNSCCUP. To report time-to-event data for local, regional and distant disease recurrence, and mortality. To assess the molecular makeup of patients with suspected HNSCCUP undergoing TBM.
Methods	
 Identification of patients prior to TBM surgery. Step serial sectioning histology performed on tongue base and tonsil tissue (if available) to compare to conventional histology results. Functional follow-up using patient completed questionnaires for pain and swallowing function (MDADI) at baseline and intervals up to 5 years. Clinical oncological follow-up recorded for up to 5 years. Exploratory molecular analysis of tongue base, tonsil (if available) and cervical metastatic tissues.
Expected outcomes	
 Increased identification of single and multi-focal primary cancers on SSS. Reasonable recovery of functional outcomes after TBM surgery prior to administration of radiation therapy. Acceptance of TBM and SSS amongst suspected HNSCCUP patients. Greater understanding of the molecular make-up of suspected HNSCCUP.

4 Signature page

The undersigned confirm that the following protocol has been agreed and accepted and that the Chief Investigator agrees to conduct the study in compliance with the approved protocol and will adhere to the principles outlined in the Declaration of Helsinki, the Sponsor's SOPs, and other regulatory requirement.

I agree to ensure that the confidential information contained in this document will not be used for any other purpose other than the evaluation or conduct of the investigation without the prior written consent of the Sponsor

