12.2 Study endpoints

For the Primary objective:

- Identification of cancer in the tonsillectomy or TBM specimen on histology.

For the Secondary objectives:

- To compare the pick-up rate of primary cancers in TBM specimens between surgical methods (robotic vs laser vs endoscopic).
 - Identification of cancer in the tonsillectomy or TBM specimen on histology.
 - We anticipate no significant disparity in pick up rate between methods with the limited number of cases in this study.
- To prospectively evaluate swallowing function and pain scores after TBM.
 - We anticipate no significant change in means from pain and MDADI scores between 0 and 6 week questionnaires. Results at 3 weeks are anticipated to be different as still recovering from surgery. Results up to 60 months will evaluate effects of any subsequent treatments and future recovery.
- To understand patient views and experiences of undergoing TBM for suspected HNSCCUP.
 - Qualitative thematic analysis therefore no quantitative end point.
- To report time-to-event data for local, regional and distant disease recurrence, and mortality.
 - Primary emergence rate of around 3% per year.
- To assess the molecular makeup of patients with suspected HNSCCUP undergoing TBM.
 - (Exploratory analysis)

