12.8 Expected Outcomes of the Study

TBM is a relatively new surgical procedure with little data relating to patients experience and recovery from this operation. The pain and MDADI questions will go some way to showing the acceptability of this procedure to patients. It is expected that by 6 weeks the pain and MDADI scores will have returned to near baseline. Most patients will go on to receive radiotherapy to their pharyngeal mucosa, which is known to worsen swallowing function. This data will go some way to clarifying that any subsequent difficulties may not be attributable to the TBM procedure.

Any increased pick up rate resulting from SSS could lead to wider adoption of this process in the management of HNSCCUP. The size of any primary sites identified through SSS over conventional histology will also be recorded and could influence the size of histological levels employed for future TBM and tonsillectomy specimens in the future management of HNSCCUP.

Data from the patient interviews and thematic analysis should help to guide patient goals for any further research in HNSCCUP. Of particular note will be the patients' wishes regarding timing of the tonsillectomy and TBM procedures, which can occur separately, particularly if initial investigation is performed in a peripheral hospital that does not offer TBM. The potential changes in management from identification of primary sites using SSS, and potential for escalation of treatment through the addition of concomitant chemotherapy will also be novel.

Results from the exploratory molecular analysis are expected to give us greater understanding of the molecular make-up of suspected HNSCCUP. Including, but not limited to, how cancers where the primary is identified differ from those primaries that remain occult, and how the cervical disease differs from primary site tissues in the oropharynx.

Results from this prospective observational study will form the foundation of a potential phase III trial investigating the roles of TBM and SSS in management of suspected HNSCCUP. The precise research question is yet to be established.

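### The denominator of the primary pick-up rate is inconsistent: Protocol 12.1 and 12.4 count specimens, 12.3 counts patients, and one patient can supply more than one specimen

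*Protocol*

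**What the plan says.** Four parts of the Protocol bear on the unit of analysis.

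- **Precision (12.1).** The section says that "initial funding limited recruitment to analysis of 60 specimens to undergo SSS", quotes a 58% pick-up rate from a meta-analysis for this cohort, anticipates about 10 points more, and raises the sample size to 100. The current precision statement begins "With 100 specimens, the 95% confidence interval boundaries around the pickup rate" and gives 9.8 points at 58% and 9.0 points at 68%.
- **Endpoint (12.2).** "Identification of cancer in the tonsillectomy or TBM specimen on histology". The text does not say whether this is one result per patient or one per specimen. The same endpoint is listed for the comparison of surgical methods, although that objective names TBM specimens only.
- **Recruitment (12.3).** "Recruitment of patients will continue until 100 patients are recruited and undergo TBM".
- **Analysis (12.4).** "The rate of CH and SSS pick up will be reported in the overall specimens", and separately by surgical method, with 95% confidence intervals. The analysis is described as descriptive only.

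On the number of specimens per patient, 9.7 states: "Where SSS is indicated (TBM and tonsil specimens, if available) the MOSES team will then send these tissues onto the RVI". Section 12.8 adds that patients' views will be sought on the "timing of the tonsillectomy and TBM procedures, which can occur separately". One patient can therefore contribute tissue from two sites, and from two operations.

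**The concern.** The figure 100 appears in two units, and the primary result is assigned to the one that the recruitment target does not control. With 100 patients and an unknown number of tonsil specimens, the specimen count can be anything from 100 upwards.

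Two analysts following 12.4 could then report different primary rates, and different absolute gains of SSS over CH, from the same slides. A specimen-level rate may also not be comparable with the 58% benchmark in 12.1, which is described as a rate for a cohort. TBM and tonsil results from one patient are correlated, so an interval that treats them as independent is not valid in general. In the breakdown by surgical method, tonsils arrive only if available and surgery follows each centre's usual practice. A difference in tonsil submission between techniques could therefore move the pooled rates by itself.

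**Working it through.** **1. Reproduce 12.1.** Inputs: n = 60 and 100, rates 58% and 68%, 95% confidence. The exact (Clopper-Pearson) interval for a single proportion gives these distances from the estimate:

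| Result | Lower arm | Upper arm | Printed |
|---|---|---|---|
| 35/60 | 13.45 | 12.60 | 12.6 |
| 41/60 | 13.29 | 11.41 | 11.4 |
| 58/100 | 10.29 | 9.80 | 9.8 |
| 68/100 | 10.08 | 8.98 | 9.0 |

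The printed values are the upper arms. For comparison, the Wald half-width 1.96 × √(p(1−p)/n) at n = 100 is 9.67 at 58% and 9.14 at 68%. All of these assume 100 independent results, which fits 100 patients counted once each. It does not fit all TBM and tonsil specimens from 100 patients unless nobody supplies a tonsil.

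**2. Effect on the rate.** Let p be the patient-level rate, t the share of patients who add one tonsil specimen, and q the share of positive patients with both specimens who are positive at both sites. Neither t nor q is in the documents. Assume that tonsil submission is unrelated to the result. Then 100 patients give 100(1 + t) specimens, of which 100p(1 + tq) are positive:

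specimen rate = p(1 + tq)/(1 + t)

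| t | q (CH) | q (SSS) | CH | SSS | Gain, points |
|---|---|---|---|---|---|
| 0 | – | – | 58.0% | 68.0% | 10.0 |
| 0.25 | 0 | 0 | 46.4% | 54.4% | 8.0 |
| 0.5 | 0 | 0 | 38.7% | 45.3% | 6.7 |
| 1 | 0 | 0 | 29.0% | 34.0% | 5.0 |
| 1 | 1 | 1 | 58.0% | 68.0% | 10.0 |
| 1 | 0 | 0.2 | 29.0% | 40.8% | 11.8 |

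In the last row, SSS = 0.68 × 1.2/2 = 40.8%. A higher q for SSS is plausible, because the project summary expects "Increased identification of single and multi-focal primary cancers on SSS". These rows are illustrations and do not bound the effect: the specimen-level gain can lie below or above the patient-level 10 points.

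**3. Effect on the interval.** Take t = 1 (200 specimens from 100 patients) and p = 0.58. Let Y be a patient's number of positive specimens, so E(Y) = p(1 + q) and E(Y²) = p(1 + 3q). The half-width that allows for clustering is 1.96 × √(Var(Y)/100)/2. The half-width under independence is 1.96 × √(r(1−r)/200), where r is the specimen rate.

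| q | Specimen rate | Clustered | Independent |
|---|---|---|---|
| 0 | 29.0% | 4.84 | 6.29 |
| 0.2 | 34.8% | 6.53 | 6.60 |
| 1 | 58.0% | 9.67 | 6.84 |

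The independence interval can be too wide, about right or too narrow.

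**4. Which unit is intended?** Several signs point to one result per patient. The primary objective concerns a primary site, which belongs to a patient. Section 12.1 equates recruitment with specimens. The planned sample size and the recruitment target are both 100. Section 17.1 costs processing per case (£30,937.50/£475.96 = 65.0 cases). Against this, 9.7 and 12.8 treat TBM and tonsil as separate specimens, and no section says that a patient's specimens count once.

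**The case against.** The strongest reply is that pooling specimens is the less natural reading. The endpoint in 12.2 reads easily as one composite result per patient, and the 58% is a cohort rate. In 12.4 the word overall stands against the breakdown by surgical method, so it may mean only that the rate is not split. On that view the stated precision is close to right and only the wording is at fault. This stands as an account of the likely intention. It does not remove the inconsistency, because 12.4 names specimens as the denominator and a later SAP would have to override it.

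A second reply is that specimen-level rows and clustered intervals are ordinary SAP content. That is correct, and their absence is not part of this point. The point is the mismatch that the Protocol itself fixes.

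A third reply is that counting patients does not remove all dependence on tonsils. Section 8.3 excludes patients whose primary was found before TBM was indicated, and 12.8 allows tonsillectomy to be a separate procedure. A tonsil removed earlier from an enrolled patient should therefore be negative by CH but can still become positive by SSS. This objection is sound, and the fix has to deal with it.

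A reader might infer more than the documents support: that the unit is nowhere named, that pooling will halve the SSS gain, or that the intervals will be too narrow. The unit is named, but inconsistently. The halved gain needs t = 1 and q = 0 for both methods. The interval error has no fixed direction.

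**Conclusion.** The point holds as an inconsistency in the denominator of the primary rate. The precision in 12.1 belongs to 100 independent results, which means one per patient. The wording of 12.4 matches that only if every patient supplies a single specimen, and 9.7 does not assume this.

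The size and direction of the effect on the rate, the absolute gain and the interval cannot be determined from the documents, because tonsil share and two-site positivity are not given and the latter may differ between CH and SSS. The 29% and 34% in the illustration rest on one tonsil specimen for every patient and one positive specimen per positive patient.

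Severity is minor to moderate. The analysis is descriptive, with no test or decision rule, and CH and SSS are read on the same tissue, so the relative gain is less affected than the absolute one.

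**What to change.** - **Unit.** In 12.1 and 12.4 replace specimens with patients. Define the primary rate as a primary identified in any submitted TBM or tonsil specimen from that patient, by CH and by SSS, n = 100 patients.
- **Precision.** The 12.1 figures then hold approximately. The exact 95% limits at n = 100 are −10.3/+9.8 points at 58% and −10.1/+9.0 points at 68%, and could be printed in that form.
- **TBM tissue alone.** Report this per-patient rate as well. It is the tissue named in the surgical-method objective, and the rate does not depend on tonsil submission.
- **Earlier tonsils.** State how tonsils removed and read as negative before enrolment are counted, since they can add to the SSS rate but not to the CH rate.
- **Specimen-level rows.** If shown, make them secondary, with intervals that allow for clustering within patient.
- **Further primaries.** List separately the number of patients already positive by CH in whom SSS finds another primary.

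The cost is wording in two sections and a few table rows, and the target of 100 patients is unchanged. The main downside is that a patient-level rate does not count a further primary in a CH-positive patient, hence the separate listing. The tissue-specific rows need the CH result for each tissue. Section 9.4 lists only CRF headings, so this may have to come from the histopathology reports already requested under 9.7.

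### SSS is run only on the tissue that CH leaves, so a stand-alone SSS rate beside the CH rate can understate what SSS adds; the plan should report added yield and the CH-or-SSS rate

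*Protocol*

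**What the plan says.** The primary objective (section 6.2) is "To establish if step serial sectioning (SSS), compared to conventional histology, improves identification of a primary site in TBM and tonsil specimens".

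Section 9.7 fixes the order of the two methods. "All tissue will undergo conventional histological processing at the local site", and this local result informs care. Then: "The following tissues will then be requested to be sent by the local teams to RMH for further analysis". On SSS itself: "The paraffin blocks supplied from TBM and tonsil specimens will undergo step serial sectioning", and "Each block will be processed in this way until the material is consumed". Steps are 0.5 mm apart, with five 4 µm sections at each. Section 9.7 does not mention re-reading the local CH slides as part of SSS, or carrying a CH-positive result forward.

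Section 12.2 defines the primary endpoint as cancer found on histology in the tonsil or TBM specimen, without saying which histology. Section 12.4 limits the analysis to description and names what will be reported: "The rate of CH and SSS pick up will be reported in the overall specimens", with 95% confidence intervals, and again by surgical method. It mentions neither a combined rate nor a paired table.

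Section 12.1 takes a pick-up rate of 58% from a meta-analysis and adds: "We anticipate a potential increase pick up rate of around 10" per cent.

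**The concern.** The two methods are not applied to equivalent tissue. CH cuts first and SSS sees what remains. The background section notes: "Smaller or involved primary foci are known to be more common in HPV related cancers". A small focus found on CH may be partly or wholly used up by the CH sections. What is left may also lie between two SSS steps. Either way the patient has a proven primary, yet a stand-alone SSS rate counts the patient as negative.

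Elsewhere the protocol describes what SSS adds to CH. Section 12.1 speaks of an increase, section 12.5 of cancers missed locally, section 12.8 of primaries found by SSS beyond CH, and the text just before section 16 of new or additional carcinomas. Two rates side by side do not give that quantity. Their difference is the patients gained by SSS minus the CH-positives not found again, and the second group has lost nothing, because CH has already identified their primary. At stake is the size of the main result, which section 12.8 intends as the foundation of a possible phase III trial.

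**Working it through.** **The plan's own figures.** Section 12.1 gives 95% limits of ±12.6 and ±11.4 points at n = 60 and ±9.8 and ±9.0 at n = 100, for 58% and 68%. These equal the upper arms of the exact (Clopper-Pearson) intervals for 35/60, 41/60, 58/100 and 68/100. Each describes one rate alone. None describes the gain.

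**Inputs.**
- C = 58%: the pick-up rate in section 12.1, taken here as the CH rate.
- g = 10 points: the increase anticipated in section 12.1, taken here as the share of all patients found by SSS only.
- m: the share of CH-positive patients in whom SSS does not find the tumour again. The documents do not give it, so a range is assumed.

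**Formulas.**
- CH-or-SSS rate = C + g = 58 + 10 = 68%, whatever m is.
- Stand-alone SSS rate = C × (1 − m) + g.
- Shortfall = C × m.
- Apparent gain = stand-alone SSS rate − C = g − C × m.

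| m (assumed) | Stand-alone SSS rate | Shortfall from 68% | Apparent gain over CH |
|---|---|---|---|
| 0% | 58 + 10 = 68.0% | 0 | 10.0 |
| 5% | 55.1 + 10 = 65.1% | 2.9 | 7.1 |
| 10% | 52.2 + 10 = 62.2% | 5.8 | 4.2 |
| 15% | 49.3 + 10 = 59.3% | 8.7 | 1.3 |
| 20% | 46.4 + 10 = 56.4% | 11.6 | −1.6 |

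The gain vanishes at m = g / C = 10/58 = 17.2%. If the true added yield were 5 or 15 points, it would vanish at 5/58 = 8.6% or 15/58 = 25.9%.

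**In patients.** Take n = 100 and suppose that 6 of 58 CH-positives are not found again (about 10%):

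| | SSS+ | SSS− | Total |
|---|---|---|---|
| CH+ | 52 | 6 | 58 |
| CH− | 10 | 32 | 42 |
| Total | 62 | 38 | 100 |

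The two separate rates are 58% and 62%, an apparent gain of 4 points. The table shows 10 patients identified by SSS alone and 68 identified in all. The added yield is 10/100 = 10% (exact 95% CI 4.9 to 17.6). Among the 42 CH-negatives it is 10/42 = 23.8% (12.1 to 39.5). Neither figure depends on m.

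**The case against.** **The counting rule is inferred.** A reader might take the protocol to say that primaries found on CH count as SSS failures. It does not say so. Section 12.4 is silent on such patients, and the add-on language elsewhere could be read as carrying CH-positives forward, in which case the shortfall is zero. This stands as a limit on the claim. It is also a reason to settle the wording.

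**The size is unknown.** A reader might infer that most of the anticipated gain will be hidden. The documents do not support that: m is given nowhere, and at 5% the apparent gain is still 7.1 of 10 points. Total loss of a focus to CH may be rare. If CH sections were also 4 µm thick (an assumption), 20 of them would use 0.08 mm, less than one-sixth of an SSS step, though trimming loss is not stated. This stands.

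**Not every discordant case is tissue loss.** Five 4 µm sections per 0.5 mm sample 20 of 500 µm, or 4% of depth. A remnant lying between steps is still in the block, so missing it is a true SSS miss. Calling every such case tumour absent from the block would hide real insensitivity. This stands, and the fix is worded accordingly.

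**SSS's own performance matters.** The objective compares SSS with CH, and section 12.8 says the results could change future histological levels. That justifies keeping the stand-alone rate, but not as the only SSS measure, since SSS was never given the tissue that CH used.

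**Extra foci are not counted.** Added yield omits further foci in CH-positive patients, which the project summary expects. True, but the endpoint in 12.2 is identification of cancer, so the two planned rates omit them as well.

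**It can wait for the SAP.** Both results are on the CRF (section 9.4), so nothing is lost for good. But section 12.4 does name the quantities to report, and they do not measure the improvement that the objective asks about.

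**Conclusion.** The concern holds in a limited form. The order of processing is explicit, and the direction follows from arithmetic: a stand-alone SSS rate cannot exceed the CH-or-SSS rate, and is lower whenever any CH-positive patient is not found again. The size rests on three assumptions: that the SSS rate is stand-alone, that 58% is the CH rate, and that 10 points is the SSS-only yield. On these, the shortfall is 58% × m, with m unknown and possibly small.

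A reader might go further and infer a wrong negative conclusion on the primary objective. The documents do not support that. Section 12.1 states that no prior sample size calculation was made and that funding set the initial number, and section 12.4 plans description only, with no test, margin or decision rule. The risk is a misleading estimate of improvement, not a failed test. It should still be corrected, because a better measure is available from data already being collected.

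**What to change.** In sections 12.2 and 12.4:

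1. Report the paired CH-by-SSS table, per patient.
2. As the main measure of improvement, give the added yield (CH-negative and SSS-positive patients as a proportion of all patients, with an exact 95% CI), and show the CH-or-SSS rate beside the CH rate.
3. Show CH-positive/SSS-negative patients separately as tumour not found in the residual block. Do not attribute them to tissue loss, since some may be true SSS misses between steps, and do not deduct them from the added yield.
4. Keep the stand-alone SSS rate as a secondary figure, labelled as describing the tissue left after CH.

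The cost is endpoint and analysis wording only; both results are already CRF fields, and no further tissue or patients are needed. The downside is that the CH-or-SSS rate cannot fall below the CH rate, so on its own it can never show SSS performing poorly. The discordant cells and the stand-alone rate must therefore always be shown with it.
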